Consent Procedures: This study involves a one-stage consent process. After confirming eligibility, participants will receive detailed information about the study and expected outcomes. Those interest will complete informed consent at the end of this information session from those willing to participate. Informed consent will be obtained from all persons interested in participating in the study by the research coordinator. This will be done in person after the potential participant is fully informed of all aspects of the research study and after the person has had the opportunity to discuss the project with his physician. The consent will be administered after a detailed study explanation by the principal investigator or the study research coordinator. Participants will then be given 30-90 minutes to read over the consent form, at which time the PI, investigators, or the study research coordinator will ask if they have any further questions. The final component of the consent process will be reviewing of a brief checklist that outlines the major aspects of the study to confirm that the subject fully understands the protocol. Participants will also be asked to review and sign a Research Subject Authorization: Confidentiality and Privacy Rights consent at the time they sign the general study consent form. This document, written to ensure compliance with HIPAA Privacy Rule guidelines, provides detailed information about what information is being collected, the participants privacy rights, and to whom the information may be disclosed. Participants will be given a signed copy of the consent forms for their records. This consent process was tested in our pilot study and has been effective. The research coordinator will obtain informed consent only after the patient demonstrates full understanding of all aspects of the study protocol. We will obtain informed consent from all focus group patient participants. We request a waiver of documentation of consent for the physician group only, since the research presents no more than minimal risk of harm to subjects and involves no procedures or activities for which written consent is normally required outside of the research context. The protocol and consent will be received and approved by the Committee on Studies Involving Human Beings of the University of Pennsylvania Institutional Review Board prior to initiating the study. It will be documented by the participant signing the consent forms in the presence of a witness. A copy of the

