
phase is critical for determining the salient characteristics of a product or service. Typically, researchers use focus groups that consist of end-users or "experts", to learn from people who have the most experience with the service, but researchers also convene focus groups of people who have little or no experience with a service to learn what may be important for a new user. Focus groups typically are comprised of 6 to 10 participants who do not know one another and who have similar associations to the topic being investigated (i.e., newly diagnosed localized PCa patients). We will make an effort to recruit equal number of surgical and radiation treatment patients and men younger than age 65 and age 65. It is recommended that one conduct at least two focus groups to capture experiences from similar groups of individuals [254-256]. Drs. [name], [name], and [name] each have extensive experience in racial and ethnic disparity research and will carefully construct each focus group. Thus, we will conduct focus groups with good representation from minority and non-minority patients. Of the six patient focus groups, three will be with newly diagnosed patients yet to make treatment decision; and three will be with those who underwent treatment one year ago, providing additional insight into what they wish they had known about the less immediate outcomes and aspects of treatment. In contrast to individual interview, focus group participants relate their experiences and reactions among peers with whom they likely share some common frame of reference. The discussions stimulated in a group setting and listening to others' experiences has the potential to stimulate memories, ideas and experiences relevant to the topic at hand [254-256]. Overarching goal of focus groups is to obtain perspectives of two of the key stakeholders (patients and physicians) about those components or features of PCa care are important to consider in choosing a treatment. The most commonly mentioned and strongly weighted features of treatment across the focus groups will be used to create the conjoint task (to be used in Phase2). If saturation of emerging themes is not reached after six focus groups, we will conduct additional focus groups until saturation occurs. (See Appendix for interview guide that was developed using results of our prior focus group of physicians, discussed in preliminary work). (3) Assigning levels to the attributes. Levels of an attribute may be cardinal (e.g. waiting time, missed work), ordinal (e.g. level of pain) or categorical (e.g. surgery or radiation treatment). Attribute levels will be identified and aligned with the active surveillance (AS) and five active treatment options being studied (RP, RALP, BT, EBRT, PT), reviewed for appropriateness and wording by the study investigators and advisory board members. (4) Developing choice scenarios. Scenarios will describe services, treatment options and outcome configurations for the attributes and level chosen. We will use a fractional factorial design to reduce the number of paired comparisons to the smallest number necessary for efficient estimation of utility weights [49,183,188]. (5) Conjoint task instrument testing. We will pilot test the conjoint task instrument for appropriateness of attributes, levels, language and ease of administration in 20 PCa patients. PHASE 2 Study Population: We will use stratified randomized control trial to study association between value markers and objective (complications and cancer recurrence) and subjective (HRQoL, psychological wellbeing) outcomes across intervention groups, over 24 month period. We will recruit newly diagnosed localized PCa patients from UPHS (Hospital of University of Pennsylvania, Presbyterian Medical Center, and Pennsylvania Hospital), Fox Chase Cancer Center and Philadelphia Veterans Administration Medical Center (PVAMC) and randomize them to conjoint analysis intervention (n=360) or control group (n=360). D.2.1.1 Participants: The sample will consist of 720 newly-diagnosed PCa patients. Inclusion criteria are: (1) treated for PCa at UPHS, Fox Chase Cancer Center or PVAMC; (2) aged 45 years; (3) newly diagnosed with localized PCa and TNM stage T3a; (4) community dwelling; (5) Gleason score 8; (6) low (PSA 10 ng/ml, Gleason 6, clinical stage T1-2a), intermediate (PSA 10 -20 ng/ml, Gleason 7, clinical stage T2b), and high risk (PSA 20, Gleason 8, clinical stage T2c-3a) group [45] and (7) provide informed consent. Exclusion criteria are: (1) Distant, metastatic or un-staged PCa at diagnosis; (2) visited the clinics to obtain second opinion only; (3) moved to another location; (4) unable to communicate in English and (5) cognitive impairment (Mini Mental State Exam or MMSE score < 21). MMSE is a standardized mental status examination widely used for clinical and research purposes [197,198]. D.2.1.2 Recruitment and participant availability: Participants will be recruited from UPHS, PVAMC and Fox Chase Cancer Center's urology and radiation oncology clinics using recruitment protocols that we have successfully used in our prior and ongoing PCa studies. Recruitment will occur in seven steps: 1) determining potential eligibility; 2) obtaining consent from patients urologist/physician; 3) confirming eligibility; 4) screening via phone and interview to assess willingness to participate; 5) obtaining informed consent and HIPAA permissions; 6) baseline assessments; and 7) follow-up assessments. The study and consent form comply with HIPAA Standards for Privacy of Individually Identifiable Health Information. The draft study design and protocol have been approved by the University of Pennsylvania IRB. Future changes will be reviewed and approved prior to implementation. Participant availability: UPHS is a large hospital and physician network in greater Philadelphia area. Approximately 1,600 patients with newly diagnosed PCa are evaluated annually: 40-50% undergo surgery (RP or RALP); 30-40% undergo EBRT

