
or BT; 10-20% undergo PT. The urology clinic at PRINCIPAL INVESTIGATOR (LAST, FIRST, MIDDLE): [name] PCORI Research Plan: Research Strategy 9 the Hospital of the University of Pennsylvania (HUP) treats more than 60% of this group; the rest are treated at Presbyterian Medical Center and Pennsylvania Hospital. Additionally, UPHS has a proton therapy center, providing a unique opportunity to study this new technology. The Philadelphia Veterans Administration Medical Center (PVAMC) cares for 33,000 veterans in Philadelphia area and evaluates ~400 patients with newly diagnosed PCa each year. Fox Chase Cancer Center evaluates ~500 patients with newly diagnosed PCa each year. Together, UPHS, PVAMC, and Fox Chase Cancer Center provide care to socio-demographically diverse population of ~2,500 men newly diagnosed with PCa each year. Thus, our study sample requirement of 720 patients (33% of the available pool) can be fulfilled comfortably, as demonstrated by the successful recruitment for our earlier studies. Recruitment: Prior to study initiation, investigators will explain the study objectives to physicians who actively treat PCa at the UPHS, PVAMC, Fox Chase urology clinics. During a patient's initial visit, Drs. [name], [name], or [name] will briefly introduce the study to the patient. Each week, the research assistant will contact the participating physician offices to obtain contact information for those patients who have expressed an interest in the study. Potential participants will be contacted during their office visits, at which time those eligible may agree to participate and provide informed consent, request additional information and/or time to think or request to be contacted later. Patients who request to be contacted later will be sent study information, a consent form and a prepaid return envelope. Participants will discuss the consent form with research assistant prior to signing, at which time all questions will be answered. During enrollment, compensation of \$20 will be provided. Using a similar recruitment strategy in our prior PCa studies, we had achieved enrollment and retention rates of 85% or higher. The expected number of 60 participants in each treatment group (AS, RP, RALP, EBRT, BT or PT) will be achieved as follows: (1) each recruited participant randomly assigned to the conjoint analysis intervention group will meet with research assistant to complete the computer-based conjoint analysis tasks and other surveys before initiation of treatment or making a treatment decision; (2) after treatment decision is made, patients (both cases and controls) will be assigned to the appropriate group based on treatment; (3) this process will continue until we reach the required number of participants in each group. To achieve this, we may evaluate and obtain baseline data including conjoint tasks from patients in excess of the required 360 participant each in the intervention and control groups. Based on our prior prospective cohort studies, to fulfill sample requirement of 60 participant in each treatment group ($60 \times 2 \times 6 = 720$), allowing for attrition we expect to obtain baseline assessment including conjoint tasks for 800 participants (10% excess). The cohort that does not get assigned for further follow-up due to targeted group enrollment accrual will be analyzed to ensure comparability. D.2.2 Process of stratified randomization: We will recruit 720 participants stratified by three hospitals-UPHS, PVAMC, or Fox Chase Cancer Center (Figure 3). [name] will create randomization sequences for each hospital using a pseudo-random number generator with random blocking and will place the treatment assignments in sealed, opaque envelopes. All investigators, staff and referring physicians will be masked to the treatment assignment, except the research assistant who will open the envelope and notify participants of group assignment. Participants will be instructed not to reveal their group status to physicians or study personnel, except in case of emergency or if necessary for medical reason, which we believe to be unlikely. D.2.2.1 Conjoint analysis intervention The primary goal of patient-centered PCa care is to engage patients and their families in meaningful and thorough interactions with their healthcare providers to develop accurate and well-conceived treatment choice, using all available medical information appropriately, while also considering the medical, social and cultural needs and desires of the patient and family. It is important for providers to solicit patient preferences and not make assumptions about which treatment and associated side effects patients are more likely to prefer or feel is best for them. Results of conjoint analysis will be shared with the participants of the intervention group, family members, and treating physicians prior to treatment decision. D.2.2.2 Usual care controls: Participants from this group will receive usual care that consists of standard educational material about various treatment options. D.2.3 Data collection and follow-up: After obtaining informed consent, baseline data will be obtained in person prior to the initiation of treatment. Participants will meet with the research assistant to complete the PRINCIPAL INVESTIGATOR (LAST, FIRST, MIDDLE): [name] PCORI Research Plan: Research Strategy 10 computer-based conjoint analysis tasks. Patient identifiers will be removed to maintain data confidentiality. Only the PI will have access to the master files. For conjoint analysis, each participant will be asked to express his preference for attributes and attribute levels for active surveillance and five active treatments for clinically localized PCa (RP, RALP, EBRT, PT, BT) based on choice sets presented. The choices will vary based on the differing attributes of various treatments ascertained in prior work and focus groups. After pilot testing and refining the conjoint task in Phase 1, final attributes and levels will be used. Trade-offs

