size based on the observed differences in outcomes such as HRQoL (SF-36 and prostate cancer index, PCI) and cost of PCa care across groups. The primary outcome is HRQoL as measured by the SF-36 and PCI sub-scales. A change of 5 to 9 points on PCI is clinically meaningful [272]. Similarly, a difference of 7 points or more on the SF subscales is considered clinically meaningful [272, 275, 301]. Based on our prior research and that of Litwin et al [253, 272], the standard deviations for the PCI and SF-36 scales in samples of men with PCa mostly range from 8 to 14; hence standardized differences (SDs) of $7/14=0.5$ to $7/8=0.87$ will be clinically relevant. The power calculations for Aims 2-4 assume availability of 720 participants who are eligible for randomization into one of the two intervention groups. We assume a conservative intra-class correlation of 0.3 and 4 follow-up measures per subject. The sample size is adjusted to accommodate a 10% missing or dropout rate by 24 months based on rates over a similar period of time in previous studies [272, 275, 301]. We assume 80% power and two-sided level of significance of $\alpha = 0.05$. We have 80% power to detect a 1.2 point difference in PCI or SF-36 sub-scale. Within treatment type, the sample size is reduced to 60 per intervention arm. We have 80% power to detect a 3.0 point difference in sub-scale with 60 patients in each arm. Thus, we will have adequate power to detect differences between treatment groups [302]. Power for identifying utility based profiles and outcomes: We analyzed the levels of power for differences in outcomes between profiles defined by latent classes of attributes-specific utilities with a conservative allocation of subjects to each profile (25 in one vs. 10 in other profile) and less conservative allocation (35 in one profile vs. 35 in other profile) using a logistic model based comparison for a binary outcome (e.g. recovery of baseline HRQoL) with a 2-sided alpha of .0125 (Holms adjustment profiles). In the first allocation, the group difference of 0.56 yields 80% power; for the second allocation an effect size of 0.42 corresponds to power of 90. Thus, with our anticipated effect size of 0.51, we will have adequate power with $n=60$ in each group. (Adjusting for patient characteristics may reduce the effect sizes of the differences between profiles.)

Key inclusion criteria

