
The following documents are currently attached to this item:

There are no documents attached for this item.

Analysis Plan

Analytic Methods General: The statistical analysis will proceed in three stages: First, we will check the data quality and carry out descriptive analyses of demographics and key outcome variables. Next, we will assess preferences using conjoint analysis and inferential analysis. For continuous outcome variables, we will check for homogeneity of errors using spread-vs.-level plots and will consider transforming variables that either are highly skewed or have variance that depends strongly on the mean. We will use methods based on general linear model (univariate and repeated-measures ANOVA, mixed models) to analyze uncensored continuous outcomes, such as generic and prostate-specific HRQoL, psychological wellbeing and satisfaction with care. For potentially censored outcome variables such as time to PSA recurrence, we will use Kaplan-Meier curves and Cox proportional hazard models. Poisson regression (zero-inflated) will be used for count data. We will use Bonferroni correction for multiple testing. We will use propensity-score and instrumental variable approach to minimize observed and unobserved bias within groups (i.e. intervention group and usual care control group). **Missing Data:** We will attempt to prevent missing data by ensuring that data collection is as complete as possible. Should there be substantial missing data, however, we will employ analysis and imputation methods to reduce bias and increase efficiency [279-282]. Based on the proportion of missing data, we will use complete-case analysis, or explore available techniques, such as standardized score imputation, simple means imputation, maximum likelihood model-based imputation, data augmentation, etc. [281]. When data are evidently non-missing at random, we will conduct explicit non-ignorable modeling and sensitivity analysis [278]. **Propensity score matching:** In observational studies, comparisons between treatment groups that do not adjust for factors associated with treatment choice may be biased. Propensity score technique offers a highly practical approach to address such bias [283]. Here, the probability of each participant being in the treatment arm (i.e., the propensity score), is estimated. Participants are sorted by their propensity scores; the sample is divided into strata based on estimated scores, the treatment effect within each stratum estimated and overall estimate computed by aggregating across strata in a weighted analysis. When the model for predicting treatment status includes all relevant covariates, within strata treatment groups will be balanced on all predictors and the overall comparison of treatment arms will have substantially lower bias. We will use a model relating PCa treatment (RP, RALP, EBRT, PT, BT or AS) to baseline factors [283-284]. To study the extent to which treatment groups are now matched, we will compare t-statistics for these covariates before and after adjusting for propensity score. This will be done separately for intervention group and usual care controls. **Instrumental variable analysis:** Another limitation of observational research is the strong potential for confounding bias, due to differences in comparison groups that are not reflected in the data (i.e., unobserved bias). The instrumental variable (IV) approach is useful in reducing this bias. This technique uses one or more observable factors that influence outcome only indirectly (the IV). This allows one to mimic randomization with different likelihoods of receiving a particular treatment [227, 285-291]. Physicians play an important role in patients treatment choice- a majority of the PCa patients report that their physicians recommendation was the most important factor in their treatment choice [11-12, 37-46, 51, 55-56, 60-64]. We will use specialty of the first physician (urologist, urologic oncologist, oncologist, radiation oncologist) who the patient saw during PCa diagnosis as an IV. We will explore other potential IVs, such as absolute distance between patients residence to the hospital where they will receive care (Hospital of University of Pennsylvania, Presbyterian Medical Center, PVAMC, Pennsylvania Hospital, or Fox-Chase Cancer Center). Validity of the IV(s) is assessed as following. First, we will use Pearsons correlation coefficient to examine the correlation between IV, primary exposure (treatment) and outcomes. We will then perform a partial F-test using a linear regression where treatment group is regressed on physician specialty along with patient attributes. For a valid IV, test statistic should be very high (e.g., physician specialty will strongly predict treatment after adjusting for covariates). Next, we will perform a partial F-test using a linear probability model in which HRQoL outcomes are regressed on specialty and patient demographic and clinical variables. For an IV to be valid, this test statistic should be very low. Finally, we will compare observable attributes across patient groups cared for by different physician specialty (initial). For the IV be valid, these groups should have comparable observable attributes. **Phase 1 Focus group analysis-development of conjoint task instrument:** The goal of focus groups is to identify attributes of PCa treatment that are most salient to localized PCa patients. This process includes following steps: (1) identifying and defining attributes; (2) assigning attribute levels; and (3) creating scenarios and choice sets. Attributes will be defined based on input from patient focus groups, literature, our prior research, and prior physician focus group. Once an attribute and its extreme values are defined, we will assign them appropriate levels. A large number of possible combinations of attributes and levels will preclude

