patients in decision (measured using CPS) using multi-nominal regression model to adjust for observed covariates. Then we will examine if these associations vary across intervention and usual care control groups. We then will repeat the model with other independent variables (decision conflict and trust). Next, we will test the association denoted by path c (direct effect of DCS, CPS, and trust on outcomes). For continuous outcomes (HRQoL, AUA-SI, MAX-PC, CES-D, SWD, and PSQ-18), we will compute area under the curve (AUC) for each measure for each patient. We will analyze AUC summaries with univariate linear models. In our main analysis we will analyze the series of functional status measures using linear mixed models that predict the outcome from time, independent variables and their interaction. We will repeat the analyses described for path c, this time by including treatment received in the models. We will test if the observed effects of DCS, CPS or trust on outcomes will be weaker after controlling for treatment. These analyses will be performed within and between groups (intervention and usual care controls). Specific Aim 3: Hypothesis: Prostate cancer patients in the intervention group undergoing conjoint analysis-value clarification exhibit improved treatment choice, satisfaction with decision, lower regrets, and improved objective and subjective outcomes. Analysis for Specific Aim 3 uses intent-to-treat approach: all randomized participants will be included regardless of whether they drop out of the intervention or study. Analysis will involve comparison of the primary outcomes between intervention and usual care control groups. Improved treatment choice is operationalized as the likelihood of low-risk PCa patients receiving active surveillance than active treatment, and will be compared between intervention and usual care control group. To allow for different trajectories of the outcome measures and to afford flexibility in making contrasts within participants over time and across participants, while simultaneously controlling for potential confounders, we propose the participant-specific or mixed effects linear model, in which the mean outcome depends on fixed covariates and random effects. The primary fixed effects will be indicators for intervention group and hospital. We will also stratify the analysis by type of treatment. The random effects represent the unobserved factors that lead to variation of the individual participants outcome. Random intercepts for each participant permit modeling of natural variation across participants at baseline. In addition, random slopes or random effects for the trajectory of each participant over time, allow for variation of each participant about a mean, overall trajectory across all participants. Although less robust to model misspecification, the mixed effects paradigm offers special flexibility in longitudinal data when exposures vary over time and when dropout and missed visits lead to unbalanced groups. The target of inference is the participant-specific response to treatment over time. At each time point of interest, we will estimate from the fitted model the difference from baseline in outcome for the treatment and control groups and test the difference between these differences. Both univariate and multivariate results will be reported in terms of Wald test, point estimates, and 95% confidence intervals. Specific Aim 4: Hypothesis 4: Prostate cancer patients whose treatment is more concordant with their values markers will experience improved subjective and objective outcomes. This specific aim s for intervention group only. We will analyze the association of the concordance between stated individual preferences and actual treatment received with objective (PCa recurrence and complications), subjective (HRQoL, psychological wellbeing, SWD, and satisfaction with care) outcomes, across treatment groups, adjusting for covariates. Association between the value markers (profiles) and measures of outcomes and personal and clinical characteristics: The value markers will be studied for their relationship with socio-demographic and clinical characteristics. We will also assess the association of value markers with outcomes. We will perform logistic regression with outcomes as the dependent variable and dummy variables for the utility-based profiles obtained earlier as independent variables. We will perform this evaluation with and without adjusting for patient attributes in the logistic model. For each case (adjusting and not adjusting for patient attributes), the evaluation of association between these profiles and outcomes will be based on a likelihood ratio test of the set of odds ratios corresponding to the dummy variables of the profiles. Additionally, we will perform a sequence of pair wise tests of comparisons of the profiles in terms of the proportion of type of treatment received based on the Holms multiple comparisons approach. This procedure is hierarchical in that it will identify the utility-based profile at the start of the process before making other comparisons, thus protecting the Type I error from additional comparisons. Specifically, Holms approach tests each pair-wise comparison in ascending order of p-values. Successively larger p-values have less rigorous alpha. The sequential Holm tests terminate after the first non-significant comparison so no subsequent comparison is significance. Concordance and its assessment: Understanding and respect for the patients preference and values is the main aspect of concordance [69, 73]. Thus a first step in concordance involves the physician extracting and understanding the patients view, followed by an agreement between the physician and patient regarding a management plan that integrates their views. There exist many definitions of concordance. For the purpose of this study, we operationalized concordance as agreement between a patients value markers and the attributes (or characteristics) of the treatment that

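### Randomisation is blocked within hospital, but Aim 3 states a hospital term only for the linear mixed model; none is stated for comparing the arms on surveillance choice, complications or PSA recurrence

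*Combined protocol and SAP*

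**What the plan says.** **Allocation.** Section D.2.2 (Process of stratified randomization) says: "We will recruit 720 participants stratified by three hospitals-UPHS, PVAMC, or Fox Chase Cancer Center". A member of the study team "will create randomization sequences for each hospital using a pseudo-random number generator with random blocking". The arms are 360 and 360.

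**Continuous outcomes.** The Specific Aim 3 text in the Analysis Plan proposes a mixed effects linear model with participant-level random intercepts and slopes, and states: "The primary fixed effects will be indicators for intervention group and hospital". This is the only hospital term in the Analysis Plan. Hospital is not among the potential confounders listed in D.2.4.4.

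**Treatment choice.** Aim 3 defines the outcome thus: "Improved treatment choice is operationalized as the likelihood of low-risk PCa patients receiving active surveillance than active treatment". The arms are to be compared on it, with no test, model or covariate named.

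**Recurrence and complications.** Both are listed under Primary outcome variable(s). The general analytic methods say that for potentially censored outcomes such as time to PSA recurrence "we will use Kaplan-Meier curves and Cox proportional hazard models", and they assign zero-inflated Poisson regression to counts. No stratum is mentioned for either. No method is named for comparing complications between arms. The later Kaplan-Meier, log-rank and Cox text concerns concordance, under Aim 4, which is confined to the intervention group.

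**The concern.** When randomisation is blocked within hospital, the arms are balanced on hospital by design. A test that leaves hospital out still counts between-hospital variation as noise, so its nominal variance is larger than the true variance of the arm difference. The plan already accepts this logic for the continuous scores, where hospital is a primary fixed effect. It does not carry it to the other randomised outcomes, and a linear mixed model with random slopes suits neither a single yes/no choice nor a time to event.

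Three outcomes are affected: surveillance choice, which leads the Aim 3 hypothesis, and complications and recurrence, which are listed as primary. The sites are a VA centre, a cancer centre and a hospital network with its own proton centre, so case mix and practice could differ, although no figure in the documents shows by how much. At stake is some power, and a choice of model left open until the data are in hand. Validity is not at stake.

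**Working it through.** **The plan's own power figures.** They concern continuous scores only. The mean of 4 follow-up measures with intra-class correlation 0.3 has variance SD² × (1 + 3 × 0.3)/4 = 0.475 SD². The plan's SDs "mostly range from 8 to 14". With SD 8 and 360 × 0.9 = 324 per arm, the detectable difference at 80% power and two-sided 0.05 is 2.80 × √(2 × 0.475 × 64/324) = 1.21 points, against the stated 1.2. With 54 per arm it is 2.97, against the stated 3.0. At SD 14 the values are 2.12 and 5.20. So the stated figures reproduce at the lowest SD. They do not bear on this point, because hospital is already in that model. No power figure is given for the arm comparison of surveillance choice, complications or recurrence.

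**Inputs for the check**
- Hospital weights: annual volumes 1,600, 400 and 500 (Accrual section), giving 0.64, 0.16 and 0.20. Using them as enrolment shares is an assumption.
- Rates by hospital: not in the documents. Those below are assumed, in the order UPHS/PVAMC/Fox Chase.
- Two-sided 0.05 and 80% power, as in the plan.

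**Formulas.** Let r = Σ w p(1−p) / [p̄(1−p̄)], the within-hospital share of the binomial variance. If the arms are balanced within hospital and the stratified test has 80% power, then for the unstratified test:
- true level = 2 × [1 − Φ(1.96/√r)]
- power = Φ(2.80 − 1.96/√r)

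Example, 20/45/40%: p̄ = 0.128 + 0.072 + 0.080 = 0.280. Within-hospital variance = 0.1024 + 0.0396 + 0.0480 = 0.1900. Total variance = 0.28 × 0.72 = 0.2016. So r = 0.9425, the level is 4.4% and the power is 78.3%.

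| Assumed rates | r | True level | Power (stratified 80%) |
|---|---|---|---|
| 30/30/30% | 1.000 | 5.0% | 80.0% |
| 25/40/35% | 0.982 | 4.8% | 79.5% |
| 20/45/40% | 0.943 | 4.4% | 78.3% |
| 15/60/40% | 0.848 | 3.3% | 75.0% |
| 10/70/50% | 0.707 | 2.0% | 68.1% |

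For less frequent events the effect is smaller. Assumed rates of 10/15/20% give r = 0.1100/0.1116 = 0.986, a level of 4.8% and power of 79.6%.

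**Simulation.** With 240 low-risk men and an odds ratio of 2.0 (both assumed), arms equal within hospital and 40,000 replicates, unstratified chi-square against Cochran-Mantel-Haenszel power was 74.5 v 74.3%, 72.6 v 72.8%, 67.2 v 69.1%, 56.9 v 63.5% and 39.0 v 54.8%, in the order of the table.

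**What adjustment does in a logistic model.** With 240 men, a conditional odds ratio of 2.0 and rates 20/45/40%, the standard error of the log odds ratio is 0.284 with hospital and 0.275 without. The marginal odds ratio is 1.92. The z values are 0.693/0.284 = 2.44 and 0.650/0.275 = 2.37. Adjustment raises power because the estimate moves away from 1, although its standard error is slightly larger.

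**Low-risk men.** Low-risk status is not a stratification factor, so blocking balances hospital only partly within this subset. At the limit of no help from blocking, the unstratified test holds its 5% level and its power is Φ(2.80√r − 1.96): 79.3%, 77.6%, 73.3% and 65.4% for the four unequal rows. So the conservatism shrinks, but a power loss of similar order remains.

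**The case against.** The strongest reply is that the plan is silent here and has not chosen unstratified tests. The Cox and Poisson sentences come from a general list of model families that gives no covariates for any of them. The same list names mixed models without hospital, and Aim 3 then adds hospital to the mixed model, so silence in the list does not show that hospital is excluded. The fixed-effects sentence could be meant for all Aim 3 outcomes. This stands: a reader might infer that the plan specifies tests that ignore the strata, and the documents do not support that. What remains is that the sentence is attached to a linear model unsuited to these outcomes, and nothing extends it.

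Second, no hospital-specific rate is given, and large effects need large contrasts. A proton centre bears on which active treatment is chosen more than on surveillance versus treatment. This also stands, and limits the claim about size.

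Third, a reader might infer that omitting hospital makes confidence intervals on the odds or hazard ratio too wide. The logistic calculation shows otherwise. A chance difference in hospital mix among low-risk men is ordinary sampling error, which the standard error already covers, and not bias.

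Fourth, recruitment to fixed numbers per treatment group leaves some randomised men without follow-up, which disturbs exact within-hospital balance. The computed levels are therefore approximate. That selection is a separate and possibly larger matter.

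**Conclusion.** The point holds as a gap with a free remedy. Hospital is a blocking factor and a primary fixed effect for the continuous scores, and no stratum-respecting model is stated for surveillance choice, complications or time to PSA recurrence.

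If hospital is left out and rates differ by site, the test is somewhat conservative, some power is lost, and the marginal odds or hazard ratio lies closer to 1. A reader might infer a threat to the type I error; the direction is the opposite, with the true level at or below 5%.

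The size rests on assumed hospital rates, volumes used as weights, and near-equal arms within hospital. The loss from 80% power is nil for equal rates, about 0 to 2 points for small to moderate differences, about 5 for large ones (15/60/40%) and about 12 for extreme ones (10/70/50%). In low-risk men the level is closer to 5% than the table shows. The levels of 3.3% and 2.0% belong to large and extreme contrasts and should not be read as the expected case.

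**What to change.** Add to the Specific Aim 3 analysis text a statement that the hospital stratum used in the mixed model also enters every other comparison of the randomised arms:
- **Surveillance versus active treatment in low-risk men, and complications:** logistic regression with hospital, or Cochran-Mantel-Haenszel by hospital. Name which of the two is the main test.
- **Time to PSA recurrence:** log-rank test and Cox model stratified by hospital.
- **Any count outcome:** a hospital term in the Poisson model.

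If odds or hazard ratios are reported, say that they are conditional on hospital.

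The cost is a sentence or two in the plan. Hospital is known at randomisation, so there are no added data, visits or sample size.
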